### **12.1.2 Selection of visits**

It is possible that more than one visit gets allocated into the same time window. In that case, only one visit will be selected for analysis tables and figures. The nonselected visit(s) will only be listed. In case an assessment gets allocated to a time window at which the assessment was not scheduled as per protocol, this assessment will not be shown in the tables or figures but will only be listed.

The visit with a DY closest to the target day will be selected. In case of ties on the same day with time not available, the assessment linked with the CRF visit will be selected for analysis.

In case more than one parameter is measured per time point (e.g. for lab), the selection is performed per parameter and per time point, not per “sample” and per time point. Missing values are removed before the selection is made.

## 12.2 General characteristics

### 12.2.1 Derivation of exposure parameters

The following exposure parameters will be derived:

- Total treatment duration = date of last study drug administration – date of first study drug administration in C203 + 14 days
- Total number of study drug doses received during C203
- Cumulative dose of study drug received: total dose of study drug in mg administered during C203
- Compliance =  $100 * (\text{total number of study drug doses actually received during C203}) / (\text{expected number of study drug doses during C203})$

Where the expected number of study drug doses is calculated as follows:

- For subjects completing the study: 52
- For subjects prematurely discontinuing the study: 1 baseline dose + integer of  $(\text{date of last study drug administration} - \text{date of first study drug administration in C203}) / 14$

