^C The Early Termination Visit is to be performed 2 weeks after the last study drug dosing for subjects who discontinue from the trial for other reasons than described in the efficacy discontinuation criteria (see section 3.2.3.2), unless they discontinue during a study visit, in which case that becomes their Early Termination Visit. For subjects who will meet the efficacy discontinuation criteria at Week 12, 24, 36, 48, 60, 72, 84 or 96, the visit at which subjects will meet these discontinuation criteria is defined as the Early Termination Visit.

^D All post baseline visits may occur at the indicated week \pm 3 days throughout the trial.

^E At the study visits at Weeks 0, 4, 8, 12, 24, 36, 48, 60, 72, 84, and 96, study drug is to be administered s.c. at the study site. At all other time points, subjects are allowed to self-administer away from the clinic. Subjects unable to have injections administered away from the study site will be required to return to the site every 2 weeks for administration of study drug by an authorized health professional.

^F Vital signs (assessment after 5 minutes in supine position) will include weight, blood pressure, pulse, and temperature. A height measurement is not required (data available from the preceding study). In case blood sampling is to be performed at the same visit, the vital signs assessment is to be performed prior to the blood sampling.

^G If TB is suspected at any time during the study, chest x-ray and interferon-gamma release assay (IGRA) should be performed.

^H Samples for routine clinical laboratory analyses will be collected predose, and include blood chemistry, hematology, acute phase proteins (C-reactive protein [CRP], erythrocyte sedimentation rate [ESR], fibrinogen) and urinalysis (urinalysis at Weeks 48 and 104). For subjects on warfarin, international normalized ratio (INR) will be performed at Weeks 0, 4, 8, 12, 24, 36, 48, 60, 72, 84, and 96, or at the Early Termination Visit.

^I At the indicated visits, samples for extended clinical laboratory analyses, including fasting serum lipids on top of the routine clinical laboratory analyses, will be performed predose. Extended clinical laboratory samples will be taken predose after the subject has been fasting for at least 10 h.

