3.3.4. STUDY DRUG INJECTIONS

At the study visits at Weeks 0, 4, 8, 12, 24, 36, 48, 60, 72, 84 and 96, study drug is to be administered s.c. at the study site. Subjects will remain at the site for 60 minutes after the injection in order to assess adverse reactions.

At all other time points, subjects are allowed to self-administer away from the clinic (after proper training in s.c. injection technique at Week 0). Subjects unable to have injections administered away from the study site will be required to return to the site every 2 weeks for administration of study drug by an authorized health professional.

All subjects are to receive 1 injection in the abdominal region at each dosing day. As injections are to be performed q2w, all injections can be performed in an abdominal quadrant of choice. However, note that the area of administration needs to be evaluable for local skin reaction (normal skin without skin burns, scars, or large tattoos in the area of administration). The abdominal quadrants used for the administrations will be recorded in the (electronic) Case Report Forms ([e]CRFs).

Detailed instructions for study drug administration are available in the Study Drug Manual.

No constraints with regard to timing of study drug administration during the day of dosing are to be taken into account. The exact times of medication dosing at the clinical site will be recorded in the (e)CRF.

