- If a subject misses a self-administration time point a new injection should be performed as soon as the patient remembers and within 1 week of the planned missed self-administration time point. If later than 1 week of the missed self-administration time point, then the CRO should be contacted. In case of rescheduling of missed visits, the total duration of the assessment period should remain 104 weeks.

If a subject misses a dose of MTX on their regularly scheduled dosing date, they should take the forgotten dose as soon as they remember; however, if more than 72 hours have elapsed since the missed dose, the subject should contact the Investigator for further dosing instructions.

For all subjects, injections should not occur less than 1 week apart. The CRO/Sponsor should be contacted if this cannot be respected. In case of interruption of more than 2 consecutive administrations, the subject should be discontinued from the study.

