## 3 STUDY DESIGN

### 3.1 Overall Study Design

This is a multicenter, open-label extension (OLE) phase II study of ALX-0061 administered s.c. in subjects with active RA who have completed the ALX-0061 treatment and assessment period of one of the preceding Phase IIb studies with ALX-0061 (C201 or C202) and who achieved at least 20% improvement in swollen joint count (SJC) and/or tender joint count (TJC) (66/68 counts) compared to baseline at the final visit of the preceding study and for the countries where there was approval for the study.

Eligible subjects will receive ALX-0061 150 mg s.c. injections, beginning at Day 1 (Week 0) of the OLE and every 2 weeks (q2w) thereafter up to and including Week 102. Eligible subjects from study ALX0061-C201 will also continue their methotrexate (MTX) treatment. Subjects will return for 12 ambulatory visits planned at Day 1 (Week 0), and Weeks 4, 8, 12, 24, 36, 48, 60, 72, 84, 96 and 104. Subjects who received study drug up to and including Week 102, should return for the End of Treatment Visit at Week 104 and for the Follow-up Visit 12 weeks after the last study drug administration at Week 102.

In the current OLE study, maintenance of the response will be reassessed at the study visits every 12 weeks from Week 12 until Week 96. Subjects who fail to maintain response and meet efficacy discontinuation criteria (< 20% improvement in both SJC and TJC

compared to baseline of the preceding Phase IIb study) will be discontinued from the study.

The schedule of assessments can be found in [Appendix 1: Schedule of assessments](#).

As this is an OLE study, blinding is not required.

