A. All assessments are to be completed prior to the study drug administration, except for subjects who discontinue study drug injections. The order of assessments if more than 1 assessment is planned at the same time should be performed according to the following principles: vital signs should be assessed prior to blood sampling; patient reported outcomes should occur prior to the physician's joint evaluation, independent joint assessment should occur prior to physician's global assessment, and study drug should be dosed after all other assessments have been performed.

B. The Baseline Visit will coincide with the 24-week End of Treatment Visit of the preceding Study ALX0061-C201, or with the 12-week End of Treatment Visit of Study ALX0061-C202. The results from the End of Treatment Visit assessments for these studies do not have to be repeated at baseline for this study, and include physical examination, vital signs, TB evaluation (questioning), routine/extended clinical laboratory analyses (at Week 22 in Study ALX0061-C201 or at Week 10 in Study ALX0061-C202), pregnancy test (urine), morning stiffness duration, joint assessment (66/68-joint count), patient pain VAS, HAQ-DI, SF-36, FACIT-F, physician and patient global assessment, concomitant medication, AEs, PK blood samples, and immunogenicity.

C. The Early Termination Visit is to be performed 2 weeks after the last study drug dosing for subjects who discontinue from the trial for other reasons than described in the efficacy discontinuation criteria (see section 3.2.3.2), unless they discontinue during a study visit, in which case that becomes their Early Termination Visit. For subjects who will meet the efficacy discontinuation criteria at Week 12, 24, 36, 48, 60, 72, 84 or 96, the visit at which subjects will meet these discontinuation criteria is defined as the Early Termination Visit.

D. All post baseline visits may occur at the indicated week ± 3 days throughout the trial.

E. At the study visits at Weeks 0, 4, 8, 12, 24, 36, 48, 60, 72, 84, and 96, study drug is to be administered s.c. at the study site. At all other time points, subjects are allowed to self-administer away from the clinic. Subjects unable to have injections administered away from the study site will be required to return to the site every 2 weeks for administration of study drug by an authorized health professional.

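### Read as truncation, the SAP's expected-dose formula for early discontinuers is one dose short whenever the last injection is 1 to 3 days early, so compliance is overstated for those subjects

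*SAP*

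**What the plan says.** SAP 12.2.1 defines compliance as 100 times doses received during C203 divided by doses expected. The expected number has two definitions:

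- Completers: "For subjects completing the study: 52".
- Early discontinuers: "1 baseline dose + integer of" (date of last administration minus date of first administration in C203) / 14.

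The section gives no rounding function, no tolerance for visit windows and no cap at 100%. SAP 4.4 names SAS as the software and adds nothing on rounding.

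Dosing runs "every 2 weeks (q2w) thereafter up to and including Week 102" (SAP 3.1). At Week 0 and at ten later visits (Weeks 4, 8, 12, 24, 36, 48, 60, 72, 84 and 96) "study drug is to be administered s.c. at the study site" (Protocol 3.3.4). On timing, "All post baseline visits may occur at the indicated week ± 3 days throughout the trial" (SAP Appendix 1, footnote D; the protocol's Schedule of Assessments has the same footnote). Protocol 3.4.1.2 measures that window from the date of the Baseline Visit. On spacing it says: "For all subjects, injections should not occur less than 1 week apart".

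Compliance is reported in SAP Table 14.1.2.5 and, with the other derived exposure data, in Listing 16.2.2.5, both on the safety population.

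**The concern.** The formula divides by 14 a number of days that the protocol allows to vary by up to 3 in either direction. Truncation treats the two directions differently. A few days late leaves the integer part unchanged, while one day early lowers it by one. Within the window the error can therefore only raise compliance, and late doses do not offset early ones.

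Two kinds of wrong value can result. A subject who took every dose is shown above 100%. A subject who missed one dose is shown at exactly 100%. Completers have a fixed denominator of 52, so a summary that pools both groups mixes two denominators, of which only one is sensitive to visit timing.

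**Working it through.** **Inputs.** Interval of 14 days, last planned dose at Week 102, the two expected-dose rules (SAP 3.1 and 12.2.1), and the ±3-day window at on-site dosing visits (Schedule of Assessments, footnote D; Protocol 3.3.4 and 3.4.1.2).

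**Reproducing the plan's own figure.** Doses every 2 weeks from Week 0 to Week 102: 102/2 + 1 = 52. The discontinuer formula at exactly 714 days gives 1 + 714/14 = 1 + 51 = 52. The two rules agree when the last dose is on schedule.

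**Last dose off schedule.** Let the last dose be due on day 14k after the first, so that k + 1 doses are scheduled. If it is given d days early, with d = 1, 2 or 3, then (14k − d)/14 = k − d/14. This lies between k − 1 and k, so its integer part is k − 1 and the formula expects k doses, one too few. If the dose is on time or 1 to 3 days late, the integer part is k and the count is right. Enumeration agrees: over the 51 possible last-dose weeks (2 to 102), all 51 × 3 = 153 early cases are exactly one dose short.

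**Size, at on-site dosing visits with the last dose one day early:**

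| Last dose | Day | Scheduled | Formula expects | All doses taken | One missed, by formula | One missed, by scheduled count |
|---|---|---|---|---|---|---|
| Week 4 | 27 | 3 | 2 | 3/2 = 150% | 2/2 = 100% | 2/3 = 66.7% |
| Week 8 | 55 | 5 | 4 | 5/4 = 125% | 4/4 = 100% | 4/5 = 80.0% |
| Week 12 | 83 | 7 | 6 | 7/6 = 116.7% | 6/6 = 100% | 6/7 = 85.7% |
| Week 24 | 167 | 13 | 12 | 13/12 = 108.3% | 12/12 = 100% | 12/13 = 92.3% |
| Week 48 | 335 | 25 | 24 | 25/24 = 104.2% | 24/24 = 100% | 24/25 = 96.0% |
| Week 96 | 671 | 49 | 48 | 49/48 = 102.1% | 48/48 = 100% | 48/49 = 98.0% |

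Two or three days early gives the same values.

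**Candidate corrections.**

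- *Nearest integer, halves up.* This returns the scheduled count for every last-dose week from 2 to 102 and every offset from −6 to +6 days. It fails at +7 days, a delay that Protocol 3.4.1.2 provides for after a missed self-injection. Six doses with the last on day 77: 77/14 = 5.5, rounded to 6, so 7 expected and 6/7 = 86% with none missed.
- *Nearest integer, halves down.* The results from −6 to +6 days are unchanged, and day 77 now gives 5, so 6 expected and 6/6 = 100%. Day 83 gives 5.93, rounded to 6, so 7 expected, as scheduled.
- *Counting scheduled dates up to discontinuation.* If the discontinuation date is an Early Termination Visit 14 days after the last dose, a last dose on day 70 and a visit on day 84 give 7 scheduled dates against 6 doses: 6/7 = 86% with none missed.

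**The case against.** **The SAP does not say truncation.** This stands. If nearest-integer rounding was intended, the error disappears. But truncation is the ordinary reading and is what the SAS INT function does, so a programmer following the text would probably truncate. The section needs an edit either way.

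**The ±3-day window covers visits, and most injections are not at visits.** This stands as a limit. Only 11 of the 52 doses are on site. For self-injections the protocol states a late allowance and a one-week minimum gap, but no early window. Subjects who meet the efficacy discontinuation criteria do so at a visit where assessments come before dosing, so their last dose would normally be the preceding one, usually taken at home. The clearest route to the error is a subject who stops for another reason after an on-site dose given early. An early home injection has the same effect, but no stated window covers it.

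**A missed dose is still visible elsewhere.** This also stands. Missed administrations go into the eCRF (Protocol 3.3.6). Number of doses, cumulative dose and treatment duration are summarised separately. Dosing records are listed (Listing 16.2.2.4), and treatment non-compliance is a category of major deviation (SAP 5.2). The missed dose disappears only from the compliance percentage.

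**A stronger reading to avoid.** A reader might infer that compliance is inflated for early discontinuers in general, or that a known share of them exceed 100%. If last-dose offsets were uniform over −3 to +3 days, 3/7 = 43% of fully compliant discontinuers would do so. Nothing in the documents supports that distribution, and the only allowance stated for self-injections is on the late side. Neither the share nor a mean inflation can be derived.

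**Conclusion.** The point holds, at minor weight. Under the ordinary reading of the formula, a last injection that is 1 to 3 days early, within the protocol's visit window, makes the expected count exactly one dose too small. Reported compliance is then 116.7% instead of 100% at Week 12 with all doses taken, or 100% instead of 85.7% with one missed. The effect is largest for the earliest dropouts and shrinks to about 2 points by Week 96.

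The conclusion rests on one assumption, that the integer is taken by truncation. It applies only to discontinuers whose last dose was early. Completers are unaffected. Compliance defines no analysis population and enters no efficacy or safety endpoint, so the consequence is confined to Table 14.1.2.5 and Listing 16.2.2.5. How many subjects are affected cannot be computed from the documents.

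**What to change.** In SAP 12.2.1, replace the integer instruction for early discontinuers with rounding to the nearest integer, and state that exact halves are rounded down: expected doses = 1 + nearest integer to (last − first administration date)/14. This still gives 52 at 714 days and gives the scheduled count for a last dose up to 6 days early or 7 days late.

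Do not switch to counting scheduled dates up to the discontinuation date, because that can add a dose that was never due to be given.

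The cost is one line of text and one line of code, with no new data. The downside is small. Reported compliance becomes slightly less favourable, and a last dose 8 to 13 days late would be charged one extra expected dose, which truncation does not do. For example, on day 78 with six doses taken, 78/14 = 5.57 rounds to 6, so 7 are expected. Protocol 3.4.1.2 already refers self-injections more than a week late to the CRO, so such cases can be identified and footnoted.

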## 12.3 Efficacy

The following assessments will be used to derive the efficacy parameters:

- Physician's assessment of tender/painful and swollen joint count: 68 joints are assessed for tenderness (TJC) and 66 joints are assessed for swelling (SJC). Joints that underwent intra-articular (IA) corticosteroid injection during the last 4 weeks will be considered as swollen and tender. Only joints that were ticked 'Yes' will be taken into account. Left and right will be summed to obtain one overall joint count.
- Physician's assessment of tender/painful and swollen joint count, selected: a selection of 28 joints are assessed for tenderness (TJC28) and for swelling (SJC28)
- Average duration of morning stiffness
- Patient's assessment of pain (100 mm) (VAS)
- Patient's global assessment of disease activity (100 mm) (VASPA)
- Physician's global assessment of disease activity (100 mm) (VASPHA)
- C-reactive protein concentration (mg/L) (CRP)
- Erythrocyte sedimentation rate (mm/h) (ESR)

- HAQ-DI (/60): 20-question instrument to assess the degree of difficulty to accomplish tasks in 8 functional areas (dressing and grooming, hygiene, arising, reach, eating, grip, walking, common daily activities) over the previous week. Responses for each question range from 0 (no difficulty) to 3 (unable to do). The score is calculated in 3 steps:
  - Derivation of the 8 category scores, by selecting the highest sub-category score
  - Adjusting for use of aids/devices and/or help from another person: scores of 0 or 1 will then be increased to 2
  - Calculating the mean of the category scores. In case less than 6 category scores are available, the HAQ-DI score will not be computed.
- SF-36 questionnaire: 36 item questionnaire that can be summarized into 8 domains (physical functioning, role limitations due to physical health problems, bodily pain, general health, vitality, social functioning, role limitations due to emotional problems, mental health) and into 2 summary measures (physical component and mental component). Version 2 of the questionnaire was used (see Section 16.6. Appendix 6)
- FACIT-F: quality of life (QOL) questionnaire consisting of 40 questions ranging from 0 to 4, grouped in 5 domains (physical well-being, social/family well-being, emotional well-being, functional well-being and fatigue). Scoring guidelines to derive subscores and total scores can be found in section 16.4.

Based on the above assessments, the following parameters will be derived:

- ACR20 response:
  - YES if ALL of the following criteria are fulfilled:
    - % improvement relative to baseline in tender/painful joint count  $\geq 20\%$
    - % improvement relative to baseline in swollen joint count  $\geq 20\%$
    - % improvement relative to baseline  $\geq 20\%$  for at least 3 of the following assessments: patient's assessment of pain, patient's global assessment of disease activity, physician's global assessment of disease activity, HAQ-DI, CRP
  - NO if not all of the above criteria are fulfilled
  - Handling of missing values:
    - if TJC or SJC are missing, ACR response will be missing
    - if any of patient's assessment of pain, patient's global assessment of disease activity, physician's global assessment of disease activity, HAQ-DI or CRP are missing, but at least 3 have a change from baseline  $\geq 20\%$  or at least 3 have a change from baseline  $< 20\%$ , ACR response can be derived, otherwise it will be missing.
- ACR50 response: definition similar to ACR20 response, but using 50% as cut-off
- ACR70 response: definition similar to ACR20 response, but using 70% as cut-off

- ACR-N index of improvement: minimum of the following 3 criteria:
  - % improvement relative to baseline in tender/painful joint count
  - % improvement relative to baseline in swollen joint count
  - Median % improvement relative to baseline of the following assessments: patient's assessment of pain, patient's global assessment of disease activity, physician's global assessment of disease activity, HAQ-DI, CRP
- $DAS28(ESR) = (0.56 \times \sqrt{TJC28}) + (0.28 \times \sqrt{SJC28}) + (0.70 \times \ln[ESR]) + (0.014 \times VASPA)$ , with VASPA measured in mm
- $DAS28(CRP) = (0.56 \times \sqrt{TJC28}) + (0.28 \times \sqrt{SJC28}) + (0.36 \times \ln[CRP + 1]) + (0.014 \times VASPA) + 0.96$ , with VASPA measured in mm and CRP in mg/L
- EULAR response is defined as follows based on the actual value of DAS28 (DAS28) in both ESR and CRP and the change from baseline in DAS28 ( $\Delta DAS28$ ) in both ESR and CRP:
  - Good response:  $\Delta DAS28 > 1.2 \text{ AND } DAS28 \leq 3.2$
  - Moderate response ( $\Delta DAS28 > 1.2 \text{ AND } DAS28 > 3.2$ ) OR ( $0.6 < \Delta DAS28 \leq 1.2 \text{ AND } DAS28 \leq 5.1$ )
  - No response ( $\Delta DAS28 \leq 0.6$ ) OR ( $0.6 < \Delta DAS28 \leq 1.2 \text{ AND } DAS28 > 5.1$ )
  - Pooled category Moderate+Good will be shown as well.
- Disease activity is defined as follows based on the actual value of DAS28(ESR):
  - Remission:  $DAS28(ESR) < 2.6$
  - Low disease activity:  $2.6 \leq DAS28(ESR) \leq 3.2$
  - Moderate disease activity:  $3.2 < DAS28(ESR) \leq 5.1$
  - High disease activity:  $DAS28(ESR) > 5.1$
  - Pooled category Remission + Low disease activity will be shown as well
- Disease activity is defined as follows based on the actual value of DAS28(CRP):
  - $DAS28(CRP) < 2.6$
  - Low disease activity:  $2.6 \leq DAS28(CRP) \leq 3.2$
  - Moderate disease activity:  $3.2 < DAS28(CRP) \leq 5.1$
  - High disease activity:  $DAS28(CRP) > 5.1$
  - Pooled category  $DAS28(CRP) < 2.6$  + Low disease activity will be shown as well
- Boolean remission is defined as follows:
  - Yes:  $TJC28 \leq 1 \text{ AND } SJC28 \leq 1 \text{ AND } VASPA \leq 1 \text{ cm AND } CRP \leq 1 \text{ mg/dL}$
  - No: else
- Clinically meaningful improvement in HAQ-DI (clinically meaningful improvement from baseline – absolute change) is defined as follows:
  - Yes:  $\Delta HAQDI \geq 0.25$
  - No:  $\Delta HAQDI < 0.25$

- Normal physical function based on HAQ-DI is defined as follows:
  - Yes:  $HAQDI \leq 0.5$
  - No:  $HAQDI > 0.5$
- CDAI score = TJC28 + SJC28 + VASPA (cm) + VASPHA (cm)
- CDAI classification:
  - Remission:  $CDAI \leq 2.8$
  - Low disease activity:  $2.8 < CDAI \leq 10$
  - Moderate disease activity:  $10 < CDAI \leq 22$
  - High disease activity:  $22 < CDAI$
  - Pooled category Remission+Low disease activity will be shown as well
- SDAI score = TJC28 + SJC28 + VASPA (cm) + VASPHA (cm) + CRP (mg/dL)
- SDAI classification:
  - Remission:  $SDAI \leq 3.3$
  - Low disease activity:  $3.3 < SDAI \leq 11$
  - Moderate disease activity:  $11 < SDAI \leq 26$
  - High disease activity:  $26 < SDAI$
  - Pooled category Remission+Low disease activity will be shown as well
- Maintained remission at Week x: remission at Week x and all consecutive time points.

MTX and corticosteroid dose related endpoints will be derived as follows:

- MTX dose decrease from baseline at W0, W48 and W104:
  - Yes: daily dose at Week 0/ Week 48 / Week 104 visit < baseline dose
  - No: else
- Discontinuation of MTX dose at W0, W48 and W104:
  - Yes: daily dose at Week 0/ Week 48 / Week 104 visit = 0
  - No: else
- Change from baseline of MTX dose at Week 0/ Week 48 / Week 104
- Change from baseline of corticosteroid dose at Week 0/ Week 48 / Week 104

